### 6.2 Subject Withdrawal

Subjects retain the right to withdraw from the Study at any time if they wish to do so, without any consequences. Should a Subject elect to withdraw from the Study, the Investigator or Site Personnel will record the reason for withdrawal in source documentation and on the appropriate CRF. In addition, the Investigator may discontinue the Subject from the study due to any of the following situations:

- Serious Adverse Event (SAE); or
- any other reason determined by the Investigator to be in the best interest of the subject.

Subjects with an ongoing AE at the time of withdrawal should be followed on study until the clinical event has been resolved or is stable if possible.

## 7.0 Procedures and Surgeries

The Amplifi System placement, operation, and removal will be done in a hospital's interventional suite or operating room. All subjects will be treated in an inpatient hospital setting. Subjects will be discharged only after Amplifi System removal with or without AVF creation.

Investigators, and other Site Personnel involved in placing, operating, monitoring, interacting

## Clinical Protocol FIH-3

Doc No: CLINP1837  
Revision: D  
DCO No: 25-009  
Effective Date: 02/06/25

with, or removing the Amplifi System, including during Study-related procedures or surgeries, will review the Amplifi System IFU and Operator's Manual prior to these activities and will refer to the Amplifi System IFU during these activities, as needed.

Please refer to Amplifi System IFU and Operator's Manual for the use and operation of the Amplifi System.

### 7.1 Amplifi System Placement

Prior to placing the Amplifi System, Investigators will review the Amplifi System IFU and Protocol for instructions on how to place the Amplifi System and will refer to the Amplifi System IFU during the placement procedure, as needed.

The Inflow Catheter will not be placed in fully occluded internal jugular veins, even after recanalization. The Inflow Catheter will not be placed in other veins such as the external jugular, subclavian, and femoral veins.

### 7.2 Amplifi System Treatment

Prior to treating Subjects with the Amplifi System, Investigators will review the Amplifi System IFU and Protocol, and will refer to the Amplifi System IFU, Operator's Manual and Protocol during treatment, as needed.

If, during the Amplifi System treatment period, a Subject has an *Amplifi System-related major hemolysis event*, the Investigator will discontinue Amplifi System treatment, provide treatment for the hemolysis, and create an AVF with the treated cephalic vein as soon as possible, if clinically indicated. Subject(s) will continue their post AVF follow-up, if applicable.

If, during Amplifi System treatment period, a Subject has experienced pump early stoppage, malfunction or deficiencies prior to the scheduled end of treatment, please refer to **Section 7.5 Pump Malfunction and Stoppage**.

### 7.3 Amplifi System Removal

Prior to removing the Amplifi System, Investigators will review the Amplifi System IFU, Operator's Manual and Protocol for instructions on how to remove the Amplifi System and will refer to the Amplifi System IFU during the removal procedure, as needed.

If a suspected thrombus is present in the Amplifi System after removal, high-resolution color photographs will be obtained of all blood-contacting components of the Amplifi System such that any thrombus present is clearly seen and documented. The Pump will be opened, the impeller removed, and photographs taken of the top bottom of the impeller and the blood contacting surfaces of the top and bottom housing.

### 7.4 Study AVF Creation

Although Study AVF creation in the distal forearm using an anastomosis surgical technique of "artery side to vein end" is encouraged, Investigators will create a Study AVF for each Subject at

## Clinical Protocol FIH-3

Doc No: CLINP1837  
Revision: D  
DCO No: 25-009  
Effective Date: 02/06/25

the location and using a technique they believe is best for each Subject.

The Protocol specifies that Investigators should create Study AVFs at the location pre-identified by the Investigator prior to enrollment. If, after Amplifi System treatment, in the Investigator's clinical judgment, creation of a Study AVF at the pre-planned location is not in the best interest of the Subject, the Investigator should create an AVF at a location that, in the Investigator's clinical judgment, is in the best interest of the Subject, if possible. If, after Amplifi System treatment, in the Investigator's clinical judgment, creation of an AVF is not in the best interest of the Subject, the Investigator should create a vascular access that, in the Investigator's clinical judgment, is in the best interest of the Subject, if possible.

\* If, at any time during Amplifi System treatment, in the Investigator's clinical judgment, creation of a Study AVF is in the best interest of the Subject, the Investigator should create an AVF.

\*\*

If the pump stops prior to the schedule end of treatment duration, please refer to **Section 7.5 Pump Malfunction and Stoppage**.

### 7.5 Pump Malfunction and Stoppage

If a Pump experiences a deficiency or malfunction and stops prior to the scheduled end of treatment (e.g., < 48 hours of treatment) and cannot be re-started:

- The patient may be scheduled for Blood Pump replacement or possible AVF creation, if clinically indicated as determined by the Investigator
- To reduce the risk of thrombus formation, the patient should continue to take apixaban anticoagulant until advised by physician to discontinue
- The Amplifi System should be removed as specified in the Instruction For Use (IFU); the Blood Pump, Inflow Catheter, and Outflow Catheters should not be flushed; and no angiography should be performed using the Access Ports.
- An ultrasound examination of the treated upper extremity will be performed to determine the amount of thrombus formation in the veins of the treated arm documented in eCRF, if any, as described in **8.1.2 Ultrasonography During Amplifi System Treatment**.
  - If thrombus is present in the treated cephalic vein and the Investigator believes the thrombus can be removed during AVF creation, then the Investigator should proceed to AVF creation, if clinically indicated. Any thrombus in the cephalic vein should be managed appropriately prior to AVF creation (e.g., using a method such as mechanical thrombectomy).
  - High resolution color photographs will be obtained of all blood-contacting components of the Amplifi System such that any thrombus present is clearly seen and documented. An investigation of the pump will be conducted per the Sponsor's Device Return Investigation procedure.
- A venogram of the treated upper extremity, central veins, and right atrium will be performed by the Investigator during Amplifi System removal, as described in **Section 8.5 Contrast Venography**.

## Clinical Protocol FIH-3

Doc No: CLINP1837  
Revision: D  
DCO No: 25-009  
Effective Date: 02/06/25

All Amplifi System unplanned stoppages, including Pump stoppages, that occur and are observed during the Study shall be documented by the Investigator and other Site Personnel by submitting a completed CRF in the Study EDC System as described in **Section 12.3**

**Amplifi System Unplanned Stoppages, Malfunctions, and Potential Device Deficiencies** and reporting as described in **Section 12.10.6 Reporting of Amplifi System Unplanned Stoppages and Malfunctions** and data analysis will be conducted as described in **Section 14.2.2 Analysis of Effectiveness Measures**.

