### Exploratory Technical Performance Measures

- **Rate of Occurrence of Amplifi System component replacement** [Timeframe: from device implantation through device removal and AVF creation]
- **Rate of Occurrence of Amplifi System treatment failure** [Timeframe: from device implantation through less than required minimum treatment hours of duration (e.g., 48 hours)]

\*Detailed definition of Treatment Failure is described in **Attachment 1: Definitions**

**Rate of Occurrence of pump stoppages and device malfunction** [Timeframe: from device implantation through device removal]

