**Table 3: Study Assessments and Actions**

Assessment or Action	Screening	Day 0 - Amplifi System Placement	Day 1 – 3 - Amplifi System Treatment	Amplifi System Removal and Study AVF Creation	Week 1,2 and Week 6 after Study AVF Creation
Duplex Ultrasonography	X	X	X	X	X
Inclusion and Exclusion Criteria	X				
Informed Consent and HIPAA Authorization	X				
Demographics and Medical History	X				
Clinical Assessment, Physical Exam	X	X	X	X	X
Laboratory Testing - Chemistry, Hematology	X	X	X	X	
Laboratory Testing – ACT		X 		X 	
Laboratory Testing – PFH, LDH, and CBC	X	X	X 	X	X
Amplifi System Blood Flow Measurement (From Recorded Amplifi System Data)		X	X	X	

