## Clinical Protocol FIH-3

Doc No: CLINP1837  
Revision: D  
DCO No: 25-009  
Effective Date: 02/06/25

B-Mode Ultrasonography During Amplifi System Treatment (by Investigator)		X	X 		
Contrast Venography (by Investigator)		X	X 	X	
Concomitant Medications		X	X	X	X
Adverse Event Logging		X	X	X	X
Determination of Study AVF Maturation (Y/N)					X
Documentation of unplanned stoppages, malfunction and deficiencies		X	X	X	
Documentation of Study AVF Thrombosis Events, Interventional Procedures, and Surgeries					X
Documentation of Access-Related Thrombosis Events, Interventional Procedures, and Surgeries (all types of access)					X

1. For Subjects that experience a prolonged Pump stoppage only
2. ACT measurements during Amplifi System placement and AVF creation per Amplifi System IFU
3. Daily testing

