## **12.3 Amplifi System Unplanned Stoppages, Malfunctions, and Potential Device Deficiencies**

All Amplifi System unplanned stoppages, including Pump stoppages, that occur and are observed during the Study, whether they are associated with an AE, ADE, SAE, SADE, or USADE, shall be documented by the Investigator and other Site Personnel by submitting a completed CRF in the Study EDC System.

All Amplifi System malfunctions and deficiencies that are related to the identity, quality, durability, reliability, safety, or performance of the Amplifi System that occur and are observed during the Study, whether they are associated with an AE, ADE, SAE, SADE, or USADE, shall

be documented by the Investigator and other Site Personnel by submitting a completed CRF in the Study EDC System. The Medical Monitor shall adjudicate device relatedness in accordance with protocol definitions.

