### 12.10.6 Reporting of Amplifi System Unplanned Stoppages and Malfunctions

Investigators will report all Amplifi System unplanned stoppages or malfunctions (including component malfunctions) on the appropriate CRF and to Sponsor as soon as possible, preferably within 48 hours, but no later than three (3) working days after Investigator or other Site Personnel becoming aware, by:

- calling Sponsor;
- emailing Sponsor; and
- submitting a completed CRF through the Study EDC System, including documentation of the call and email to Sponsor.

After notifying Sponsor (or Sponsor delegate) and Medical Monitor of an Amplifi System unplanned stoppage or malfunction, Investigators will provide a written report of the Amplifi System unplanned stoppage or malfunction to Sponsor and Medical Monitor within five (5) working days of the unplanned stoppage or malfunction through the Study EDC System.

Investigators will also report all Amplifi System unplanned stoppages and malfunctions to the Central EC in accordance with the EC requirements.

Sponsor will report all Amplifi System unplanned stoppages and malfunctions to the appropriate regulatory agencies and bodies in accordance with relevant local, regional, and national regulatory requirements.

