## Clinical Protocol

### FIH-3

Doc No: CLINP1837  
Revision: D  
DCO No: 25-009  
Effective Date: 02/06/25

procedure or surgery, inclusive of percutaneous injection of an agent intended to induce thrombosis.

- *Site Personnel* is defined as persons employed by the Site, other than Investigators, that are involved in the storage, placement, use, operation, maintenance, care, cleaning, monitoring, interaction with, removal, and disposal of the Amplifi System and its components.
- *Thrombophilia* is defined as a clinical tendency to thrombosis or molecular abnormalities of hemostasis that predispose to thrombosis.
- Treatment Failure is defined as “a subject will be classified as a treatment failure if they do not achieve the minimum required Amplifi treatment duration of 48 hours. This classification applies regardless of whether the subject has an arteriovenous fistula (AVF) created or not.”
  - **Device technical success** is defined as successful operation of the Amplifi system throughout the treatment period (from device implantation through device removal and AVF creation) without unplanned pump stoppages or device malfunctions that require intervention or prevent completion of the intended 48-hour treatment duration.
  - **Treatment success** is achieved when the Amplifi system operates without unplanned pump stoppages or device malfunctions, allowing for the full 48-hour treatment duration, and results in successful creation of an arteriovenous fistula (AVF) or meets the predefined clinical objectives as specified in the study protocol.
- *Vascular access for hemodialysis* is defined as an AVF, AVG, or hemodialysis catheter.
- *Vascular access-related hospitalization* is defined as admission to a hospital for treatment of a vascular access or a vascular access-related complication, not inclusive of a visit to an emergency room, clinic, or outpatient facility that does not result in admission to a hospital.
- *Vascular access steal syndrome* is defined as one or more signs or symptoms of ipsilateral hand ischemia that requires treatment with an interventional procedure or a surgery.
- *Wrist or distal forearm radiocephalic AVF* is defined as an AVF made with the radial artery and the cephalic vein, wherein the anastomosis is made in the hand, wrist, or distal forearm.

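### Documentation of pump stoppages is limited to stops that are observed, and the recorded System flow data are never used to confirm or complete the count

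*Protocol*

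**What the plan says.** **How stops enter the data.** Section 7.5 of the protocol reads "All Amplifi System unplanned stoppages, including Pump stoppages, that occur and are observed during the Study shall be documented by the Investigator" and other site staff, "by submitting a completed CRF in the Study EDC System". Section 12.3 uses the same limit: "All Amplifi System unplanned stoppages, including Pump stoppages, that occur and are observed during the Study, whether they are associated with an AE" or not. Section 12.10.6 starts the reporting clock at awareness: "no later than three (3) working days after Investigator or other Site Personnel becoming aware". The Section 7.5 sentence then refers the analysis to Section 14.2.2, which names no data source for stoppages.

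**What else is collected.** Table 3 has a row labelled "Amplifi System Blood Flow Measurement (From Recorded Amplifi System Data", marked for placement, Days 1-3 of treatment and removal. A different row, "Documentation of unplanned stoppages, malfunction and deficiencies", covers the CRF record. The two are not linked.

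**What depends on the count.** Section 4.5 lists "Rate of Occurrence of pump stoppages and device malfunction" among the exploratory technical performance measures. Appendix 1 says that treatment success "is achieved when the Amplifi system operates without unplanned pump stoppages or device malfunctions", with the full 48 hours of treatment and either AVF creation or the protocol's clinical objectives also required. Section 14.2.2 plans modelling of predictors of treatment success.

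**The concern.** The outcome definitions are wider than the route by which stops are captured. The stoppage measure and treatment success refer to stoppages without qualification, while the documentation duty covers only stops that someone observes. Treatment success sets no minimum duration and does not ask whether the stop needed intervention, so one short stop that resolves by itself defeats it. That is also the kind of stop staff are most likely to miss.

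The error has one direction. A missed stop lowers the stoppage rate and can raise the success rate; nothing about an unnoticed stop works the other way. Pump reliability is a live question for this device. The Summary in Section 3 reports that some Subjects in the earlier study needed pump replacement, and that the assembly process was changed afterwards. A possible check on the count is already among the data collected, yet the protocol gives it no role.

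**Working it through.** The protocol states no expected stoppage rate, success rate, power or alpha, so there is no figure of its own to reproduce. The check compares the texts and then sizes the effect.

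**1. Capture against outcome**

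| Item | Limited to observed stops? | Effect of a brief unseen stop |
|---|---|---|
| Stoppage CRF (7.5, 12.3) | Yes | No CRF |
| Reporting (12.10.6) | Starts at awareness | Not reported |
| Stoppage rate (4.5) | No | May be undercounted |
| Treatment success (Appendix 1) | No | Subject may be scored a success |
| Device technical success (Appendix 1) | No, but tied to stops needing intervention or preventing completion | Little |
| Treatment failure (Appendix 1) | Not applicable; defined by under 48 hours of treatment | None directly |

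The exposure is therefore confined to the stoppage rate and treatment success.

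**2. Effect of one missed Subject**

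The protocol enrols up to 10 Subjects. Reading the rate as a per-Subject proportion, one Subject whose only stop goes unseen changes it by 1/10 = 10 percentage points. Treatment success changes by the same 10 points if that Subject meets its other conditions. With fewer than 10 Subjects the step is larger.

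Exact (Clopper-Pearson) 95% intervals at n = 10 show how the reported result would differ:

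- 0/10: 0 to 1 − 0.025^(1/10) = 0.3085, about 31%
- 1/10: 0.3% to 44.5%
- 2/10: 2.5% to 55.6%

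The intervals overlap widely. What changes is mainly the reported point estimate, for example from no stops to one or two affected Subjects.

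**3. Illustration of frequency (assumptions, not document figures)**

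Let p be the true proportion of Subjects with a stop and s the share of those Subjects whose stop is detected. The expected observed rate is p·s. The chance that at least one of 10 Subjects is wholly missed is 1 − (1 − p(1 − s))^10. For p = 20%:

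| s | Expected observed rate | Chance of at least one missed Subject |
|---|---|---|
| 90% | 0.20 × 0.90 = 18% | 1 − 0.98^10 = 18% |
| 70% | 0.20 × 0.70 = 14% | 1 − 0.94^10 = 46% |
| 50% | 0.20 × 0.50 = 10% | 1 − 0.90^10 = 65% |

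Over p from 10% to 50% and s from 50% to 90%, the observed rate runs from 5% to 45% and the chance of at least one missed Subject from 10% to 94%. A range this wide shows only that the frequency cannot be fixed from the protocol.

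**The case against.** The strongest reply is that Sections 7.5, 12.3 and 12.10.6 set a documentation duty for staff and do not define the numerator of any rate. The outcome definitions are not limited to observed stops. A stop found while reading the recorded flow could itself count as observed and prompt a CRF. The source for an exploratory rate, and any reconciliation rule, could also sit in the SAP, which is not at hand. This stands as far as it goes. A reader might infer that stops are counted only when they are on a CRF, or that recorded data are excluded, but the protocol says neither. What remains is that the only capture rule it states is the observed-only one, and that Section 7.5 passes that record to an analysis section naming no other source.

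Second, detection should be good. All Subjects are inpatients until removal (Section 7.0), the System has alarms (Section 15.4), and ultrasound is at least daily with treatment running (Section 8.1.2). This also stands: long stops are unlikely to be missed, so the exposure is mainly brief ones. For the same reason the protocol does not support a fear that imaging for thrombus would be lost. Ultrasound and venography at the end of treatment are specified whether or not a stop occurred (Sections 8.1.3 and 8.5.5).

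Third, the recorded data may not settle the matter. A reader might take Table 3 to mean continuous logging throughout treatment in which every stop shows as loss of flow. Table 3 marks study periods only; it gives no sampling interval and does not say that brief stops can be identified. Low recorded flow could also come from a sensor fault or a planned pause. This argues for reconciling the two sources rather than replacing the CRF count.

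Finally, the stoppage rate is exploratory, and treatment success is an Appendix 1 definition used in the modelling rather than a measure listed in Section 4.5. That limits the weight of the point.

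**Conclusion.** The point holds in limited form. The protocol restricts stoppage documentation to observed events and gives the recorded System flow data no part in confirming or completing the count. Brief unnoticed stops may be missing from the exploratory stoppage rate and from the assessment of treatment success. Each affected Subject is worth 10 percentage points at n = 10, in the direction of a more reliable device.

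This assumes that the rate is a per-Subject proportion, that the analysis follows the capture rule as written, and that the record can show at least some stops that staff miss. The number of missed stops is unknown; the ranges above are illustrations. Treatment failure is not directly affected and device technical success is barely affected. The documents do not establish that results will be biased, nor by how much. This is a cheap improvement to an exploratory measure, not a flaw that undermines the study.

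**What to change.** In Sections 7.5 and 12.3, delete the restriction to observed stops and add wording to this effect:

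> Each Subject's recorded System data, from pump start to removal, will be reviewed for loss of flow as far as the record allows and reconciled with the stoppage CRFs. Planned pauses and sensor faults will be excluded. The reconciled count will be used for the stoppage rate and for treatment success; the CRF-only count will be reported alongside.

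A cross-reference from the stoppage measure in Section 4.5 and from treatment success in Appendix 1 would make the source plain. If the record cannot resolve brief stops, the report should say so.

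The cost is a short text change and review of at most ten Subjects' recorded data. The stoppage rate may look slightly worse. No clinical rule changes.

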## 8.0 Study Assessments and Follow Up

The total duration of Subject participation in the nonrandomized cohort will be **up to 6 weeks** after AVF creation. **Table 3** summarizes Study assessments and actions and **Table 4** summarizes the assessment window.

**Table 3: Study Assessments and Actions**

Assessment or Action	Screening	Day 0 - Amplifi System Placement	Day 1 – 3 - Amplifi System Treatment	Amplifi System Removal and Study AVF Creation	Week 1,2 and Week 6 after Study AVF Creation
Duplex Ultrasonography	X	X	X	X	X
Inclusion and Exclusion Criteria	X				
Informed Consent and HIPAA Authorization	X				
Demographics and Medical History	X				
Clinical Assessment, Physical Exam	X	X	X	X	X
Laboratory Testing - Chemistry, Hematology	X	X	X	X	
Laboratory Testing – ACT		X 		X 	
Laboratory Testing – PFH, LDH, and CBC	X	X	X 	X	X
Amplifi System Blood Flow Measurement (From Recorded Amplifi System Data)		X	X	X	

